3.9 Intervention Administration

A total of 50 Latino advanced cancer patients will be enrolled in this study and randomly assigned to the intervention (n=25) or control (n=25) condition. Pre-intervention, patients'

communication goals will be assessed. Then, patient will participate in the intervention or a usual care control condition. After participating in the intervention or control condition, patients' engagement in ACP will be assessed to determine if the intervention improved ACP engagement and planning.

The intervention itself will be administered by a fully trained, licensed social worker via telephone. This interventionist will use a culturally competent communication intervention to "coach" patients in how to be motivated for and to actually engage in ACP, and will be bilingual in Spanish and English.

Patients randomized into the control group will receive usual care. For usual care, patients will engage in standard care with no modifications. Thus, ACP discussions will only occur as they do in usual clinical care (i.e. brought up in clinical encounters).

3.10 Special Concerns

Patients who agree to participate in the study and provide informed consent will be asked to complete an intervention and post-intervention assessment. Assessments will occur within a few weeks of study enrollment. Each patient assessment will be scheduled to take place at a time and a location that is convenient for the participant, and will take approximately 30 minutes to complete. Patient assessments are designed to be focused and brief. The assessment batteries are less lengthy than those for a prior, similarly designed study (Coping with Cancer), for which rates of incomplete assessments were extremely low, with no interviews of patients requiring rescheduling, and with minimal missing data.

3.11 Compensation

Patient participants will each receive \$25 (gift card) compensation for each completed survey assessments (2) for a total of up to \$50. The issue of compensation is addressed in the respective consent forms. This amount was selected to compensate patients for their time without coercion to enrollment in the study. UTSW participants will receive their gift cards via mail, by the Fred Hutch team following survey and assessments completed over the phone.

4. Registration Procedures

4.1 Subject Registration (FHCC and Sub-sites)

Subjects will be registered within OnCore CTMS as per the standard operating procedure for Subject Registration.

5. Study Procedures

5.1 Schedule of Assessments

Table 1. Schedule of trial events

	Baseline	Post-intervention (with 1 week of completing intervention)	3 mos. after completion of intervention	Off Study
Informed consent	X			
Demographics	X			
Clinical variables				X
Acceptability		X		
Usability		X		
Feasibility		X		
Quality of life	X	X		
Cultural beliefs (Fatalismo, personalismo, respeto)	X	X		
Familial beliefs (Familismo, filial duty)	X	X		
Religious/spiritual beliefs (Religious coping, religious beliefs about end-of-life medical care)	X	X		
Terminal illness acceptance	X	X		
Illness understanding	X	X		
Readiness for ACP	X	X		
Engagement in ACP	X	X		
Healthcare utilization	X	X	X	
Goal-concordant care	X	X	X	

6. Data Reporting / Regulatory Considerations

6.1 Data Collection

The source of the data to be collected will be verbally administered surveys and (with patient consent) extraction of data from medical records. All materials outlined here will be used specifically for the purposes described in this proposal and not for any other purpose. All data collected during the study will be de-identified. Participants will be informed that all responses will be kept confidential. Data will be linked to participants' names only by means of an assigned study identification number. Authorized study staff are the only individuals who will have access to participants' identification numbers and personal information. This information will be stored in a password protected database on the secure FHCC server as well as in hard copy format in a locked file cabinet in a locked office that is only accessible to the study PI and relevant study staff. The files linking participant study identification numbers to participant names will be destroyed after study completion. All necessary precautions will be taken to ensure that there is no breach of confidentiality.

Participants' completed interviews and self-report measures will be saved in a password protected file on the secure FHCC network server (electronic format) or stored in a locked file cabinet in a locked office (hard copy format) accessible only to the PI and relevant study staff. Participants' responses will be entered into a password-protected electronic database for analytic purposes. This database will be stored on the secure FHCC network server that is password protected.

Data will be obtained by experienced research staff trained in interviewing study participants. All study staff involved in the research will be educated on the protection of human research participants, including attending formal training in the Responsible Conduct of Research provided at FHCC (for FHCC study staff) and UT Southwestern (for UT Southwestern study staff). All personnel involved in the proposed protocol will be educated regarding HIPAA regulations and will fully understand their responsibility to safeguard the personal health information of every participant involved in the research. The data will be used specifically for the purposes outlined in this proposal or a subsequently IRB approved protocol and not for any other purpose.

***Additional measures to protect participants in the in-person interviews or usability testing from COVID-19 related exposure and infection.** In-person interviews will only be conducted in line with all the safety regulations and recommended procedures for vulnerable and at risk patient populations. As such, no in person approaches will happen prior to the appropriate approval and authorization at each participating site. In the even in person approaches are approved, study personnel will ensure proper PPE is worn by approaching study staff, proper social distancing is observed, and that all patients consent to and are comfortable with in person interviews. Due to potential risks, telephone based interviews will be promoted among participating patients.

6.1.1 REDCap

All data will be entered and stored securely on FHCC REDCap servers.

6.2 Regulatory Considerations

6.2.1 Institutional Review Board/Ethics Committee Approval

As required by local regulations, the Investigator will ensure all legal aspects are covered, and approval of the appropriate regulatory bodies obtained, before study initiation.

Before initiation of the study at each study center, the protocol, the ICF, other written material given to the patients, and any other relevant study documentation will be submitted to the appropriate Ethics Committee. Written approval of the study and all relevant study information must be obtained before the study center can be initiated or the IP is released to the Investigator. Any necessary extensions or renewals of IRB approval must be obtained for changes to the study, such as amendments to the protocol, the ICF, or other study documentation. The written approval of the IRB together with the approved ICF must be filed in the study files.

The Investigator will report promptly to the IRB any new information that may adversely affect the safety of the subjects or the conduct of the study. The Investigator will submit written summaries of the study status to the IEC/IRB as required. On completion of the study, the IRB will be notified that the study has ended.

The Investigator will not modify or alter this protocol without the agreement of the IRB. All agreed protocol amendments will be clearly recorded on a protocol amendment form and will be signed and dated by the original protocol approving signatories. All protocol amendments will be submitted to the relevant institutional IRB for approval before implementation, as required by local regulations. The only exception will be when the amendment is necessary to eliminate an immediate hazard to the trial participants. In this case, the necessary action will be taken first, with the relevant protocol amendment following shortly thereafter.

Once protocol amendments or consent form modifications are implemented at the lead site, FHCC, updated documents will be provided to participating sites. FHCC must approve all consent form changes prior to local IRB submission.

Relevant study documentation will be submitted to the regulatory authorities of the participating countries, according to local/national requirements, for review and approval before the beginning of the study. On completion of the study, the regulatory authorities will be notified that the study has ended.

6.2.2 Ethical Conduct of the Study

The Investigators and all parties involved should conduct this study in adherence to the ethical principles based on the Declaration of Helsinki, GCP, ICH guidelines and the applicable national and local laws and regulatory requirements.

This study will be conducted under a protocol reviewed and approved by the applicable ethics committees and investigations will be undertaken by scientifically and medically qualified persons, where the benefits of the study are in proportion to the risks.

6.2.3 Informed Consent

The investigator or qualified designee must obtain documented consent according to ICH-GCP and local regulations, as applicable, from each potential subject or each subject's legally authorized representative prior to participating in the research study. Subjects who agree to participate will sign the approved informed consent form and will be provided a copy of the signed document.

The initial ICF, any subsequent revised written ICF and any written information provided to the subject must be approved by IRB prior to use. The ICF will adhere to IRB requirements, applicable laws and regulations.

Informed Consent will occur under the IRB of FHCC and UT Southwestern.

At UTSW, verbal consent will be obtained from recruited participants who give consent. A waiver for documentation has been approved by Fred Hutch and UTSW IRB.

6.2.4 Compliance with Trial Registration and Results Posting Requirements

The following refers to the proposed project, which will be considered a clinical trial according to NIH standards. This dissemination plan is consistent with NIH Guide Notice NOT-OD-16-149. [name] (PI) will register the proposed trial on ClinicalTrials.gov prior to recruiting and consenting the first participant. All study results from the trial will be submitted to ClinicalTrials.gov no later than 12 calendar months after the trial's primary completion date. [name] (PI) will review all ClinicalTrials.gov entries for accuracy and comprehensiveness prior to submission for review.

Compliant with NIH policy, all informed consent documents for the pilot trial will include a statement that these results will be made available at the ClinicalTrials.gov website after the initial analysis is complete. Additionally, all participants will be informed that study findings will be presented in aggregate form and that participant-level and identifying information will not be included to ensure confidentiality.

FHCC has an internal policy to ensure that clinical trials registration and results occur in compliance with policy requirements. Specifically, the FHCC ClinicalTrials.gov administrator will facilitate the Principal Investigator's dissemination of study results through ClinicalTrials.gov registration and reporting. [name] will be responsible for handling ClinicalTrials.gov requirements for this project according to FHCC ClinicalTrials.gov policy. Once a record is established, [name] will confirm accuracy of record content; resolve problems; and maintain records including content update and modifications. [name] will also be responsible for results reporting and Adverse Events reporting at the conclusion of the project.

6.2.5 Record Retention

Essential documents are those documents that individually and collectively permit evaluation of the study and quality of the data produced. After completion of the study, all documents and data relating to the study will be kept in an orderly manner by the Investigator in a secure study file. Essential documents should be retained for 2 years after the final marketing approval in an ICH region or for at least 2 years since the discontinuation of clinical development of the IP. In addition, all subject medical records and other source documentation will be kept for the maximum time permitted by the hospital, institution, or medical practice.

7. Statistical Considerations

Participants (N=50) will be randomly assigned to the intervention group (n=25) or the control group (n=25). They will then complete measures of engagement in ACP post-intervention. Feasibility and acceptability will be examined with frequency and descriptive statistics (i.e., mean, median, standard deviation, range) for enrollment rates, number of sessions completed, number of weeks required to complete the intervention, and Likert-scale items assessing satisfaction with the intervention and perceived helpfulness. Because this is a pilot study, in accordance with published standards for pilot feasibility clinical trials,⁵⁴ inferential statistics on measures of feasibility ($\geq 70\%$ intervention completion rates) and acceptability ($\geq 70\%$ rate it as "helpful" or "very helpful") are not recommended. Rather, we will examine the average rates of completion

as well as satisfaction and helpfulness ratings to determine feasibility and acceptability based on those values being equal to or greater than 70%. We will also conduct qualitative analyses on the open-ended questions related to helpfulness. Thematic analysis using an iterative process will be conducted for all qualitative analyses.⁵⁵⁻⁵⁹ A coding scheme and codebook will be created to analyze transcripts of the responses to the open-ended question. Transcripts will be coded separately by two individual coders for manifest (e.g., frequencies) and latent (e.g., underlying themes) variables. If discrepancies occur, a third coder will resolve these conflicts. Interviews will continue until thematic saturation is achieved.^{60,61} Based on our prior field testing of interventions with patients with advanced illness, we anticipate reaching saturation with n=10 participants. Thus, n=25 in the experimental condition should be well powered to reach thematic saturation.

To examine potential efficacy, preliminary analyses will utilize t-tests to compare the two groups on baseline characteristics (e.g., education, age). Using a criterion of $p < .10$, any variables that are different among the groups will be included in the final logistic regression models as potential confounders. To test the study aim, five separate logistic regression models will be run in which ACP outcomes (yes/no to EOL discussions with family and providers; and the completion of advance directives DNR, health care proxy, and living will) will be predicted by the group variable (CCC intervention vs. control). The statistical power of the proposed logistic regressions to detect a minimum odds ratio of 2.0 for dichotomous outcome measures of ACP, for a two-tailed test with power $(1 - \beta)$ equal to 0.80, and $\alpha = 0.05$, requires a sample size of 113. Our proposed sample size of n=50 will be underpowered if the effect size is small but adequately powered if it is large. However, this study is a preliminary pilot and the main focus and goal of this is to determine feasibility, acceptability, and to provide preliminary data to inform a fully-powered RCT in future research (R01 submission).

7.1 Randomization. We will utilize stratified randomization at the level of each site to ensure balance across the interventional and control groups at the level of each site. To randomize, we will employ a random number generator to randomize participants to study arms at the level of each site. To ensure randomization was effective, separately for each binary outcome, we will perform a two-sample proportions test to test if the rate of outcomes is significantly different between intervention and control groups. Separately for each continuous outcome, we will perform a two-sample unpaired t-test or unpaired Wilcoxon test (as appropriate) to test if the rate of outcomes is significantly different between intervention and control groups.

7.2 Missing data. To reduce missing data, study staff will conduct interviews rather than relying on written self-reports. This approach has been used previously in our prior work to help reduce data that is missing due to patients accidentally overlooking or missing items or requiring clarification of certain terms (e.g., what is an advance directive). Due notice is taken to ensure that patients know that they are free to skip items they prefer not to answer.

8. Adverse Event Reporting Requirements

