Analytic Plan:	SPSS version 23.0 will be used to conduct all quantitative statistical analyses. Participants (N=50) will be randomly assigned to the culturally competent communication intervention group or PLAN (n=25) or the control group (n=25). They will then complete measures of engagement in ACP post-intervention. Preliminary analyses will utilize t-tests to compare the two groups on baseline characteristics (e.g., education, age). Using a criterion of $p < .10$, any variables that are different among the groups will be included in the final logistic regression models as potential confounders. Five separate logistic regression models will be run in which ACP outcomes (end-of-life care discussions with family and providers; and the completion of advance directives DNR, health care proxy, and living will) will be predicted by the group variable (intervention vs. control). The statistical power of the proposed logistic regressions to detect a minimum odds ratio of 2.0 for dichotomous outcome measures of ACP, for a two-tailed test with power $(1 - \beta)$ equal to 0.80, and $\alpha = 0.05$, requires a sample size of 113. Our proposed sample size of n=50 will be underpowered if the effect size is small but adequately powered if it is large.

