3.4 Exclusion Criteria

Patient exclusion criteria: (1) not fluent in English or Spanish; (2) severely cognitively impaired (as measured by Short Portable Mental Status Questionnaire scores of ≥ 6 to be delivered by trained study research staff during screening);⁴¹ (3) too ill or weak to complete the interviews (as judged by interviewer); (4) currently receiving hospice at the time of enrollment (to allow prediction of ACP); (5) children and young adults under age 18; and (6) patients deemed inappropriate for the study by their treating oncologist. Because the primary outcomes include both completion of advance care planning documentation as well as conversations around ACP, we have chosen not to add exclusion criteria around completion of advance directives. The goal of PLAN is two-fold – which is to increase completion of these documents but also to increase engagement in conversations around ACP with loved ones and providers (which can be present or not present despite completion of documents).

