3.6 Interviews, Focus Groups, Surveys, and/or Observations

A. Administration

- *Timing and Frequency*

Pre-interview/baseline assessment, intervention, and post assessment follow up post-intervention (within a week).

- *Location*

Telephone-based delivery of the intervention and in person or over the phone assessments. Cancer patients may opt to have their interview(s) during infusion at participating sites (FHCC, UT Southwestern/PHHS, Confluence Health).

***Additional measures to protect participants in the in-person interviews or usability testing from COVID-19 related exposure and infection.** In-person interviews will only be conducted in line with all the safety regulations and recommended procedures for vulnerable and at-risk patient populations. As such, no in person approaches will happen prior to the appropriate approval and authorization at each participating site. In the even in person approaches are approved, study personnel will ensure proper PPE is worn by approaching study staff, proper social distancing is observed, and that all patients consent to and are comfortable with in person interviews. Due to potential risks, telephone-based interviews will be promoted among participating patients, when available.

- *Person Identifiers*

Clinical variables will be collected from medical records and will include the following: cancer diagnosis and stage, treatment received, co-morbid conditions (i.e., Charlson Comorbidity Index, CCI), and Karnofsky performance status.

B. Study Instruments

Feasibility will be measured by intervention completion (Benchmark: $\geq 70\%$ complete the intervention sessions). Acceptability will be measured by a single-item question assessing helpfulness of the intervention (1 = not at all helpful, 5 = very helpful) as well an open-ended question about helpfulness of the intervention (“What was helpful about the intervention?”) (Benchmark: $\geq 70\%$ rate it as “helpful” or “very helpful”). Demographics will be measured via self-report assessing: age, gender, race, ethnicity, marital status, employment status, education, income, religion, insurance coverage, national origins (e.g., Mexican), cultural heritage, and acculturation.⁴² Clinical variables will be assessed using records from medical charts and will include the following: cancer diagnosis, treatment, site, and stage; co-morbid conditions, and Karnofsky⁴³ performance status.

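### Covariates for the five efficacy models are chosen by baseline t-tests at p<.10 from an open list, so the baseline value of the ACP outcome would usually be left out, and site is not a model term

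*Combined protocol and SAP*

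**What the plan says.** - **Selection rule.** In section 7, "preliminary analyses will utilize t-tests to compare the two groups on baseline characteristics (e.g., education, age"), and at p<.10 "any variables that are different among the groups will be included in the final logistic regression models as potential confounders". The Analytic Plan in the Protocol Summary has the same rule. Group is the only predictor fixed in advance in the five models.
- **Candidates.** Education and age are examples, not a list. Section 3.6 collects 13 self-reported demographics, beginning "age, gender, race, ethnicity, marital status, employment status, education, income, religion, insurance coverage". It also names terminal illness acceptance and illness understanding as potential confounders, but section 7 does not mention them.
- **Baseline ACP status.** Section 3.4 states "we have chosen not to add exclusion criteria around completion of advance directives". Table 1 in section 5.1 schedules "Engagement in ACP" at baseline and post-intervention. Section 3.9 gives the purpose of the post-intervention assessment as "to determine if the intervention improved ACP engagement and planning". No section puts the baseline value in the models or restricts them to patients without the directive.
- **Site.** Section 7.1 stratifies randomization by site. No section makes site a model term.
- **Purpose.** Section 7 says "the main focus and goal of this is to determine feasibility, acceptability, and to provide preliminary data to inform a fully-powered RCT".

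**The concern.** In a randomized trial, a baseline difference at p<.10 reflects chance. The rule therefore brings in variables because they happen to be imbalanced, whether or not they predict the outcome. Two analysts who screen different lists could fit different models. The named screen, a t-test, also does not suit nominal variables such as race, religion or insurance.

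The strongest candidate predictor of having a directive or a discussion after the intervention is having had one before it. That variable is not barred, but it enters only if it is among those screened and happens to be flagged. An imbalance too small to be flagged can then pass into the estimated effect. What is at stake is the quality of the preliminary efficacy estimates that are to inform the later trial.

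**Working it through.** **The plan's own figure.** Section 7 gives N=113 for an odds ratio of 2.0 (two-sided alpha 0.05, power 0.80). This is not reproduced for a 1:1 binary group: over control rates from 2% to 89%, the smallest total is 266. That is a separate matter. Only the odds ratio of 2.0 is used here.

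**Inputs.** From the documents: 25 per arm, p<.10, and Latino background rates in section 2 (32% discussions, 9% living will, 4% proxy). Assumed, because the documents do not give them: the share positive at baseline, the share of those still positive afterwards (persistence), and conversion among the rest.

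**1. Chance covariates.** With k independent null variables, P(at least one enters) = 1 − 0.9^k: 19% for k=2, 65% for k=10, 72% for k=12 (the section 3.6 demographics that can vary, since all patients are Latino) and 88% for k=20.

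**2. Is baseline ACP status flagged?** Let a and b be the baseline positives per arm, each Binomial(25, π). Sum P(a)P(b) over all pairs with t-test p<.10. Count unflagged gaps the same way.

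| π | Flagged | Unflagged gap of 3 or more patients | Unflagged gap of 5 or more |
|---|---|---|---|
| 9% | 11.0% | 9.8% | 0.004% |
| 20% | 10.4% | 27.0% | 1.7% |
| 32% | 10.1% | 34.7% | 7.0% |

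**3. What an unflagged gap can do.** 11/25 v 6/25 gives p=.141 (not flagged); 12/25 v 6/25 gives p=.080 (flagged). Take 11 v 6, no intervention effect, and 15% of the rest converting in both arms. The expected post-intervention gap is (5/25) × (persistence − 0.15): 20 × 0.45 = 9 points at 60% persistence, and 20 × 0.80 = 16 points at 95%.

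**4. Power, plan rule v site plus baseline value.** The simulations use 25 per arm, 10 variables screened (baseline status plus nine noise variables) and Firth fits throughout. Scenario A has 20% positive at baseline and 15% control conversion; B has 32% and 10%. At an odds ratio of 2.0, intervention conversion is 2p/(1+p): .30/1.15 = 26% in A and .20/1.10 = 18% in B. The large effects are 50% in A, odds ratio (.50/.50)/(.15/.85) = 5.7, and 45% in B, odds ratio (.45/.55)/(.10/.90) = 7.4.

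| Persistence | A, OR 2.0 | A, OR 5.7 | B, OR 2.0 | B, OR 7.4 |
|---|---|---|---|---|
| 60% | .087 v .103 | .505 v .552 | .058 v .072 | .376 v .436 |
| 80% | .080 v .110 | .487 v .582 | .056 v .068 | .352 v .497 |
| 95% | .082 v .114 | .497 v .647 | .047 v .077 | .361 v .594 |

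At an odds ratio of 2.0 the gain is 1 to 3 points in this table (3,000 trials per cell; standard error near a power of .10 is √(.10×.90/3000), about 0.5 points). Separate runs with the baseline term alone widen this to about 1 to 4. For the large effects it is 5 to 23 points (2,000 trials per cell, standard error about 1.1 points). There, omitting site moved the result by at most 1.2 points, so the gain comes from the baseline value.

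**5. Cost of the rule itself.** In the large-effect runs the rule is 0.5 to 3.7 power points below no adjustment. Its p<.05 verdict differs from the unadjusted one in 8% to 12% of trials.

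**6. Type I error.** Null rejection is .019 to .044 under the plan, .037 to .054 unadjusted and .019 to .046 with site plus baseline.

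**7. Sparse cells.** If the section 2 rates apply, 25 controls have no event with probability .96^25 = 36% (proxy) or .91^25 = 9.5% (living will). The maximum-likelihood odds ratio is then infinite if the other arm has an event. Ordinary fits with the baseline term failed in about 21% to 80% of simulated trials. In a rare-outcome null (4% at baseline, 4% v 4% converting), Firth with site plus baseline rejects in .007 of trials, against .027 under the plan, so that model becomes very conservative.

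**The case against.** The case on the other side is mainly about size, and much of it stands.

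- At the plan's only stated effect, no analysis has useful power (roughly .05 to .13), and the gain is a few points.
- The 11 v 6 example lies at the edge of what escapes the flag. Such gaps are rare at 9% prevalence, about half would favour control, and even the 16-point spurious difference gives p of about .25 on expected counts.
- Site added no power in the runs, which assumed no site effect. Its inclusion rests on the stratified design, and two site terms are hard to support with very few events.
- The 72% figure assumes independent tests, whereas income, education, insurance and employment are plausibly correlated.
- Section 3.6 does name two potential confounders, so a closed model must say what becomes of them.
- Section 7.1 compares outcomes between arms as a check on randomization. This may be loose wording for a baseline comparison.
- Background rates may understate events here, because directive holders are admitted and one site recruits through a palliative care clinic.

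The pilot purpose lowers the weight but does not answer the point. The Protocol Summary places potential efficacy within the primary objective and lists no exploratory objectives, and section 7 carries these estimates forward to the next trial. None of these objections makes chance imbalance a sound way to choose covariates.

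**Conclusion.** The point holds as a cheap improvement that should be made. The rule selects chance imbalances from an open list and would include baseline ACP status in only about 10% to 11% of trials at 9% to 32% prevalence. The benefit of changing it is precision and reproducibility of the preliminary estimates: about 1 to 4 power points at an odds ratio of 2.0, and about 5 to 23 only if conversion odds ratios are about 6 to 7. Both ranges assume persistence of 60% to 95%, equal in both arms.

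Three stronger readings are tempting, and the documents support none of them. A reader might infer that the rule inflates false positives; under the plan, null rejection stayed at or below .044. A reader might take the 23-point figure as the expected loss; the only effect size in the documents is 2.0, and they give no persistence. A reader might conclude that the pilot's main aims are compromised; feasibility and acceptability are judged against descriptive 70% benchmarks and do not use these models. Confidence is high on the text and lower on the size.

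**What to change.** In section 7 and the Analytic Plan, delete the p<.10 rule and state that:

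- each model includes group, the baseline value of the same ACP outcome (dropped if it does not vary) and site, with site omitted by a pre-stated rule when events are too few;
- models are fitted by Firth penalised logistic regression with profile-likelihood intervals;
- unadjusted risk differences with 95% confidence intervals are reported alongside;
- baseline characteristics are shown by arm without significance tests;
- terminal illness acceptance and illness understanding are used in a stated way, for example only in a sensitivity analysis, or not used.

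The Protocol Summary says "SPSS version 23.0 will be used to conduct all quantitative statistical analyses"; allow other software where needed. In section 3.6, have the chart review also record directives already present at consent, since its stated window begins at consent. In section 7.1, say whether the tests concern baseline or post-intervention values; tests of post-intervention outcomes cannot check randomization.

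The cost is wording in these sections, minor programming and possibly one chart item. Site and self-reported baseline engagement are already collected. The downside is that chance imbalances in other variables are shown but not adjusted for in the main models.
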